8.2.3 Pre-planned sensitivity or exploratory analyses

As sensitivity analysis in group C, PFS and OS analyses will also be presented in the intent to treat population.

As exploratory analysis, in group A and B, baseline frailty scores will be correlated with safety, tolerability and efficacy.

In all groups, correlation of molecular markers including MYC, MCL-1, CDK9 and CDK5 proteins level (but not exhaustively) with response, success, PFS and OS will be explored.

8.2.4 Prognostic factor analyses

Data of this trial will be added to the EORTC GBM data warehouse for further research projects (e.g. pooled analyses of prognostic factors).

8.2.5 Data recording and display

Frequency tables will be tabulated (by treatment group or otherwise) for all categorical variables by the levels of the variables as they appear on the CRF (with %). Categories with a text field specification will be tabulated as categories and then supplemented by a listing with the following information for the patients fulfilling the condition for the specification (patient id, institution, treatment group, value of the item and text field contents).

Dates relating to events prior to entry will be presented as the delay in days (or weeks, months, or years) between the past event and the date of entry (date of enrollment – date of past event + 1) and presented using the median and range. For example, on the enrollment checklist, the date of last administration of prior treatment (or the date of first diagnosis of the cancer) will be presented as the time elapsed (in days, weeks, months or years, as appropriate) since the day of the last administration and the date of entry on study (date of enrollment – last administration/diagnosis +1).

Other delays (e.g. re-treatment delays) are presented as continuous variables using the median and range.

Continuous variables for which a coding system exists (such as for laboratory data) will be recoded into categories (for adverse events, the grading scale specified in the protocol will be used). Whenever no specific scale exists, laboratory data will be categorized based on the normal range: for example, below the lower normal limit (when appropriate), within the normal range, above the upper normal limit (ULN) and the degree to which it is above the ULN (for example $> 2.5 \times$ ULN, $> 5 \times$ ULN, $> 10 \times$ ULN). For laboratory data, the nadir is generally displayed. The nadir in a given cycle is the lowest laboratory value in that cycle; the overall nadir for a patient is the lowest laboratory value among all cycles.

Other continuous variables (for example age, dose ...) are presented using the median and range (minimum, maximum).

If appropriate, continuous data may also be presented in categories (for example, age may also be grouped in decades).

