dosing) will be taken prior to combination with TMZ in each cycle, with the rationale of depleting anti-apoptotic proteins in human tumors *in vivo*, too. Because TG02 and TMZ may have overlapping toxicities, TG02 will not be dosed on weeks 2 and 3 of each cycle to allow patients a recovery period prior to the next course of treatment.

Original starting dose: as described above, the MTD of TG02 in combination with carfilzomib was 250 mg. TMZ is a new combination agent with TG02. Therefore, the original starting dose for TG02 in combination with TMZ was 200 mg, one dose level below the MTD from the Multiple Myeloma study combining TG02 with carfilzomib.

Adjusted starting dose: As described above, an IDMC reviewed the data for the first 24 patients of Group C. The IDMC made a recommendation to change the dosing cohorts for Group B. We agreed with the recommendation and incorporated these in the amendment to protocol version 4.0.

Therefore, a new dosing cohort of 100 mg TG02 is being added for Group B. Patients being enrolled to this study will start in this cohort. If the safety profile in that cohort is acceptable (i.e., meets the criteria described in Section 5.2.1, the dose will be escalated to the next cohort, 150 mg TG02.

Group C

Schedule: TG02 will be dosed twice a week for 4 weeks of a 28-day schedule.

Original starting dose: as described above, the MTD of TG02 in combination with carfilzomib was 250 mg. Therefore, single agent TG02 was initially dosed at 250 mg in this group.

Adjusted starting dose: In Group C, 24 patients were enrolled and treated with single agent TG02. The frequency and severity of neutropenia in the first 6 patients was higher than expected and the starting dose was reduced to 200 mg. Eighteen (18) patients were enrolled and treated at 200 mg. The frequency of some AEs, specifically Grade 3 or 4 neutropenia and Grade 3 or 4 liver enzyme elevations, was still higher than previously observed in the multiple myeloma studies with TG02. An Independent Data Monitoring Committee (IDMC) reviewed the data for the first 24 patients of Group C. The IDMC made a recommendation to change the starting dose for patients in Group C. We agree with the recommendation and are incorporating it in this amendment to protocol v 4.0.

Therefore, the new starting dose for TG02 in Group C is 150 mg.

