8.2.2 Statistical methods

Group A and B

Primary endpoints are the determination of the Maximum Tolerated Dose (MTD) and the recommended phase II combination dose. All analyses will be performed in the safety population. Analyses will be descriptive only presented with tables and listings (i.e. no formal inference). Objective response rate will be reported with exact (binomial) 95% two-sided confidence interval. The PFS-6 and OS-9 and the medians will be extracted from their Kaplan-Meyer curves. The 95% two-sided confidence intervals will be computed based on the Greenwood's formula and based on the Reflected Method for the median. The best overall response will be presented in contingency table with numbers and percentages. The objective response (CR+PR) and complete response (CR) rates will be reported with exact (binomial) 95% two-sided confidence interval. Duration of objective response and complete response will be estimated using Kaplan-Meier methodology. Median duration of objective and complete response with corresponding 95% two-sided confidence interval provided by the Reflected Method will be displayed. Hematological and biochemistry parameters will be presented with clinical significance (CS vs NCS).

Safety and efficacy data in patients excluded from the safety population will be reported separately.

Group C

- Number of patients free of progression at 6 months (primary analysis)

In the efficacy population:

All patients will be observed during a minimum follow-up of 6 months. The number of patients free of progression and alive at 6 months will be computed and the above-mentioned decision rule applied. Patients lost to follow-up or who died before 6 months are considered as failures at the time of analysis. In case more than 45 eligible patients are recruited, the decision rule will be applied as such on the first 45 eligible patients. The proportion of patients free of progression at 6 months will be presented with 80% two-sided confidence intervals computed based on the Exact Binomial distribution.

- Progression free survival

In the efficacy population:

The primary endpoint, PFS rate at 6 months (PFS6) and the median PFS will be extracted from the Kaplan-Meyer PFS curve. For PFS6, 80% two-sided confidence intervals and 95% two-sided confidence intervals will be computed based on the Greenwood's formula. For the median the Reflected Method will provide 95% two-sided confidence intervals.

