Laboratory events of clinical significance (CS) will be reported on the adverse events CRFs and will be reported separately.

- Hematological parameters

The worst value of each hematological category will be identified and graded for each patient.

Frequencies and percentages of each category will be tabulated. A table with grade 3/4 frequencies and percentages will also be displayed. The frequencies and percentages of patients with at least one grade 1 or one grade 3 or 4 hematological toxicity will be presented.

- Biochemistry parameters

The worst value of each biochemical category will be identified and graded for each patient. Frequencies and percentages of each category will be tabulated. A table with grade 3/4 frequencies and percentages will be displayed. The frequencies and percentages of patients with at least one grade 1 or one grade 3 or 4 biochemistry toxicity will be presented.

- All adverse events

The worst grade of each AE item will be identified for each patient. Frequencies and percentages of each category will be tabulated. Tables with all grades, grades 3 or 4 and grades 5 frequencies and percentages will be displayed. The frequencies and percentages of patients with at least one grade 1 or one grade 3 or 4 or one grade 5 AE will be presented.

- Related AEs

The worst grade of each likely related AE item will be identified for each patient. Frequencies and percentages of each related AE category will be tabulated. Tables with related grades, grades 3 or 4 and grade 5 frequencies and percentages will be displayed. The frequencies and percentages of patients with at least one related grade 1 or one related grade 3 or 4 or one related grade 5 AE will be presented.

- SAEs and Related SAEs

After reconciliation with the SAEs listing extracted from the EORTC pharmacovigilance database, the worst grade of each (related) serious AE category will be identified for each patient. Frequencies and percentages of each category will be tabulated. Tables with all (related) grades, (related) grades 3 or 4 and (related) grades 5 frequencies and percentages will be displayed. The frequencies and percentages of patients with at least one (related) grade 1 or one (related) grade 3 or 4 or one (related) grade 5 SAE will be presented.

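### Section 8.2.5 displays the lowest laboratory value for every analyte, which understates toxicity wherever harm is a high value and conflicts with 7.3.2 and 8.2.2

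*Combined protocol and SAP*

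**What the plan says.** Section 8.2.5 (Data recording and display) applies to the whole trial. It states the rule and its per-cycle definition together: "For laboratory data, the nadir is generally displayed. The nadir in a given cycle is the lowest laboratory value in that cycle". It then adds that "the overall nadir for a patient is the lowest laboratory value among all cycles". No analyte is exempted. The same section says laboratory data are recoded into categories: by the protocol's grading scale where one exists, and otherwise by the normal range, including "the degree to which it is above the ULN", with example cut-points of 2.5, 5 and 10 x ULN.

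Two other sections point in the toxic direction. Section 8.2.2, in the safety text under the Group C heading, says "The worst value of each biochemical category will be identified and graded for each patient" and adds a grade 3/4 table. Section 7.3.2, which is not limited to any group, has headquarters compute the highest CTCAE grade for each cycle and each patient.

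For Groups A and B, the laboratory text in 8.2.2 is a single sentence: "Hematological and biochemistry parameters will be presented with clinical significance (CS vs NCS". It does not say which value is shown.

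**The concern.** The nadir is the right summary for neutrophils, platelets and hemoglobin. It is the wrong end of the scale for ALT, AST, bilirubin, alkaline phosphatase, creatinine, LDH and creatine kinase, all of which are in the biochemistry panel of section 6.2. For sodium, potassium, calcium, magnesium, phosphate and glucose it shows only one of the two ends that matter.

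Liver tests are not incidental here. Section 1.3.3.2 names the events whose frequency led to the dose changes as "specifically Grade 3 or 4 neutropenia and Grade 3 or 4 liver enzyme elevations". Section 5.2.1.2 lists hepatotoxicity among the expected overlapping toxicities of TG02 and TMZ. It reports grade 3-4 ALT elevation in 4 of 12 patients in another TG02-TMZ study, at different doses and on a different TMZ schedule, so that figure is context only. The DLT definition also leaves out laboratory abnormalities that are asymptomatic or reversible and can be rapidly controlled. The laboratory tables are one of the places where a reader would look for such rises.

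**Working it through.** The plan states no figure on this point, so there is none to reproduce. The check compares the rules and then works through an illustration.

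**1. The rules for an analyte that rises.**
- 8.2.5, nadir sentences: minimum per cycle and minimum overall, all groups.
- 8.2.5, category text: degrees above ULN, which a minimum will rarely fill.
- 8.2.2 under Group C: worst value, graded.
- 8.2.2 for Groups A and B: clinically significant or not, with no choice of value.
- 7.3.2: highest CTCAE grade per cycle and per patient, all groups.

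Two programmers, one following 8.2.5 and one following 8.2.2, would produce different ALT tables.

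**2. What the plan's own limits imply.** Section 3.1 requires ALT and AST of at most 2.5 x ULN within 7 days before the first dose. If the pre-dose sample counts as part of cycle 1, the overall minimum will almost never exceed 2.5 x ULN, whatever happens later. Section 8.2.5 does not say whether that sample counts. In addition, the Group B hepatotoxicity table allows TG02 to be re-introduced after a grade 3 event only once it has improved to grade 1 or less. A re-treated patient therefore has a later low value for the overall nadir to select.

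**3. Illustration.** The ALT values below are assumed, in x ULN. Cycle 1 has days 1, 8, 15 and 22 (the Group C schedule; Group A stops at day 15 and Group B adds day -7). Cycles 2 and 3 have one value each. Nadir = minimum; worst = maximum.

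| Pattern | Cycle 1 | Cycle 2 | Cycle 3 | Per-cycle nadirs | Overall nadir | Overall nadir without day 1 | Worst |
|---|---|---|---|---|---|---|---|
| Transient | 0.8, 3, 7, 2 | 1.0 | 0.9 | 0.8, 1.0, 0.9 | 0.8 | 0.9 | 7 |
| Late | 0.8, 0.9, 1, 1 | 2 | 12 | 0.8, 2, 12 | 0.8 | 0.9 | 12 |
| Sustained | 1.2, 4, 7, 6 | 6 | 4 | 1.2, 6, 4 | 1.2 | 4 | 7 |

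Reading the table against the 8.2.5 cut-points:
- Transient: a value above 5 x ULN is shown as not above ULN, both per cycle and overall.
- Late: the cycle 3 value of 12 is shown per cycle, because it is the only sample, but the overall nadir of 0.8 hides it.
- Sustained: the rise is understated but not absent, at 1.2 overall, or 4 if day 1 is treated as baseline, against a worst value of 7.

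**4. Where the loss occurs.** Sampling is weekly in cycle 1 and, under 6.2.4.1, once per 28-day cycle afterwards. From cycle 2 the per-cycle nadir normally equals the single observed value. The loss is therefore in the overall nadir, in cycle 1, and wherever unscheduled samples are taken.

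**The case against.** The strongest reply is that nothing important depends on this display. Section 7.3.2 gives a toxic-direction rule for all groups, so 8.2.5 is not the sole rule bearing on Groups A and B. Section 7.3.1 has every adverse event recorded, with a new entry when severity changes. For Group C, the specific worst-value rule in 8.2.2 can reasonably be read as overriding a general display sentence. Section 8.2.5 says only that the nadir is generally shown, and its above-ULN categories suggest that high values were meant to be visible. Groups A and B will also have listings. All of this stands, and it limits the point to a display.

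It does not remove the point. The qualifier permits exceptions but names none, so the direction of a safety summary is left to whoever programs it. Section 7.3.2 governs grades, not which laboratory value is displayed. For Groups A and B, the clinical-significance split does not supply that rule either.

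A reader might go further and infer that the recommended phase II dose would be chosen with liver toxicity hidden. The documents do not support that. Under 5.2.1 and 8.1.1 the MTD follows from DLT counts in cycle 1, and DLTs are investigator-assessed events. In Group B, 5.2.1.2 also sends the 100 mg and 150 mg data to the IDMC when the DLT criteria are not met at 150 mg, but nothing says that review relies on the 8.2.5 display. Nor do the documents support a percentage of patients whose liver toxicity would be missed: that would need assumed ALT distributions and spike patterns which they do not give.

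**Conclusion.** The point holds as an internal inconsistency in a safety display. Read literally, 8.2.5 shows the least toxic value for analytes whose toxicity is a rise, and one end only for two-sided analytes. It disagrees with its own above-ULN categories, with 8.2.2 under Group C and with 7.3.2. The understatement can be complete for a transient rise (7 shown as 0.8 x ULN in the assumed series) and partial for a sustained one. It is confined to the overall nadir, cycle 1 and unscheduled samples. Groups A and B are the most exposed, because 8.2.2 gives them no worst-value rule. Endpoints, DLT decisions and graded adverse event analyses are unaffected. The conclusion rests on following the wording of 8.2.5 as written; the size shown is illustrative.

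**What to change.** Replace the nadir sentences in 8.2.5 with one rule for all three groups, for example:

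*For each laboratory parameter, the worst value in the direction of toxicity is displayed per cycle and overall: lowest for blood counts and albumin; highest for ALT, AST, bilirubin, alkaline phosphatase, creatinine, LDH and creatine kinase; both for electrolytes and glucose.*

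State that this is aligned with 7.3.2 and with the worst-value text in 8.2.2, and extend that text to Groups A and B. Say whether the pre-dose cycle 1 sample counts as on-treatment. Any panel test not named above, such as urea, total protein or the coagulation tests, should be assigned a direction in the same list.

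The cost is a change of wording and one extra table row for each two-sided parameter. No new data are needed.

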8.3 Interim analyses

No interim analysis will be done.

8.4 End of study

End of study occurs when all of the following criteria have been satisfied:

1. Thirty days after all patients have stopped protocol treatment
2. The trial is mature for the analysis of the primary endpoint as defined in the protocol
3. The database has been fully cleaned and frozen for this analysis

9 Trial Governance and Data Monitoring

9.1 Study committees

9.1.1 Study Management Group (SMG)

The Study Management Group is set up for this study. It consists of the EORTC Headquarters team in charge of running the study (clinical research physician, statistician, clinical scientist, clinical operations manager and data managers) and the principal study coordinator.

The EORTC Headquarter team is responsible for the day-to-day conduct of the trial. The Study Coordinator will assist the team in case of problems with patient evaluation (eligibility, treatment compliance, safety).

The Study management Group also performs the medical review as indicated below.

9.1.2 Study Steering Committee (SSC)

The Study Steering Committee for this study is composed of the study coordinators, the representatives of Academic Groups collaborating to the study, at least one representative of the EORTC Headquarters (Study Clinical Research Physician or Clinical Scientist) and one representative of the Sponsor, if the sponsor is not the EORTC.

This committee provides the general oversight of the study and has the executive power. The SSC monitors study progress and conduct and advises on its scientific credibility. The SSC will consider and act, as appropriate, upon the recommendations of the independent data monitoring committee.

9.1.3 Independent data monitoring committee (IDMC)

The independent data monitoring committee for EORTC studies (IDMC) is in charge of the independent oversight of this study. The composition of the IDMC is described in EORTC Policy "Independent Data Monitoring Committees for EORTC studies" (ref. EORTC POL004) and its functioning is ruled by the charter annexed to the Policy.

The study-specific experts on the IDMC performing this review will be selected for their relevant expertise with the disease and/or treatments assessed in the study.

The IDMC reports its recommendations in writing to the Study Management Group through the clinical operations manager to the Study Steering Committee and other relevant parties (supporting bodies, collaborative groups...).

9.2 Data Monitoring

9.2.1 Monitoring during medical review meetings

The medical review will be performed on a regular basis by the clinical research physician assisted as needed by the study management group. The main study coordinator will, in particular, support the Study Clinical Research Physician during the medical review process and will assist the team in case of problems with patient evaluation (safety, eligibility, treatment compliance). The main study coordinator is also responsible for the review and approval of the medical review plan and medical review reports.

For blinded trials, the medical review is conducted blinded to treatment allocation.

If at any time during the course of the study, the medical review identifies safety signals or other elements that could affect the potential risks and benefits to the study participants. These will be reported to the Study Steering Committee and may trigger a review by the EORTC Independent Data Monitoring Committee (IDMC).

9.2.2 Monitoring by the IDMC

The IDMC will be asked to give advice on whether the accumulating data from the trial justifies continuing recruitment of further patients or further follow-up.

The IDMC will review the trial whenever safety problems or other elements are identified during the medical review or by the SMG and/or SSC that could affect the potential risks and benefits for study participants.

The IDMC will also review the intermediate reports of accumulating data according to the study interim monitoring plan described in the statistical section of this protocol. If a decision is made to continue without change, the IDMC may advise on the frequency of future reviews of the data on the basis of accrual and event rates.

While the trial is ongoing the accumulating data will generally remain confidential, unless the SSC and IDMC agree that the data should be made public.

10 Quality of life assessment (Groups A and B only)

10.1 Rationale

Health-related quality of life (HRQoL) is a multidimensional construct, which can be defined as a state of general well-being reflecting physical, psychological, and social well-being and the impact of the disease and/or treatment related symptoms on daily-life functioning. The patient's subjective perspective is an inherent component of HRQoL and is therefore best assessed via self-administration.

Reducing mortality and morbidity is still the most important goal in cancer clinical research. Nevertheless, issues such as reducing side effects, symptom relief and improving patients' satisfaction have also become relevant parameters in the evaluation of medical strategies. Cancer treatments may produce adverse effects and diminish a patient's HRQoL even when survival is extended. Progress in the acceptance of new cancer therapies is sometimes critically dependent on their HRQoL consequences.

Due to the poor overall prognosis of the study population in this study (i.e. frail, elderly high-grade glioma patients) improvement of the well-being during the remaining survival is an important factor for the patient.

10.2 Objective

Since elderly patients are more prone to side-effects from novel treatments and since maintaining HRQoL is a major consideration in de-escalating treatments that provide little benefit, e.g., TMZ in patients with tumors without MGMT promoter methylation, this phase Ib trial will also capture data on HRQoL in Group A (addition of TG02 to postoperative RT in MGMT-unmethylated, IDH1^{R132H}-non-mutant WHO grade III and IV glioma) and B (addition of TG02 to postoperative TMZ chemotherapy in MGMT-methylated IDH1^{R132H}-non-mutant WHO grade III and IV glioma). Therefore, in the present study, HRQoL is an exploratory endpoint.

The main objective of this study is to explore the impact of combined treatment on overall global health and HRQoL in this fragile, elderly (> 65 years) high-grade glioma patient population. A secondary objective is to evaluate the effect of the treatment on the remaining symptoms and functioning scales as treatment-related side-effects may have a (temporary) negative influence on the health related domains of HRQoL of these patients with a particular emphasis on fatigue, nausea/vomiting and diarrhea in the light of the expected side effects of TG02.

